Analgesic use: Use of analgesics to control oral pain (parenteral, per oral, or transdermal) will be examined by displaying number and percentages of subjects in each treatment group taking: 1) topicals, 2) OTC analgesics, 3) PO opioids, 4) parenteral opioids. Also, PO and parenteral opioids will be combined to form a category for all opioids. Treatment group differences in proportions will be evaluated using a Chi-square test.

Exploratory Efficacy Endpoints

The effects of AG013 will be explored further on the basis of the following:

This document contains confidential information. It is intended solely for the use of the principal investigator, co-investigators, staff, appropriate institutional review boards or ethical committees, and other required regulatory bodies.
Descriptive statistics will be presented for the incidence of severe mucositis (WHO grades 3 or 4) within subgroups receiving each of the following cumulative radiation doses: 30 Gy, 40 Gy, 50 Gy and 60 Gy.

For each subject, oral mucositis severity scores (WHO grades 0-4) at each time point will be used to calculate area-under-the-curve (AUC) using the trapezoidal rule. Average AUC severity-by-time curves will be generated and plotted for each treatment group, and compared using the Wilcoxon rank-sum test.

Genomic characteristics of responders will be summarized and compared with non-responders.

Frequency and duration of RT interruptions: The number of subjects in each treatment group with an unplanned break in radiotherapy during the 7- to 9-week regimen will be tabulated. Subjects with an interval of 5 days or more without an administration of radiotherapy, or who discontinue radiotherapy prior to completing the planned RT regimen, will be considered to have an unplanned break in RT. The duration of unplanned RT interruptions (in days) will also be summarized by treatment group using descriptive statistics. For subjects who prematurely discontinue radiotherapy, the time from the last dose of RT to the prescribed end date of the regimen will be used in the calculation. The number of unplanned office visits, ER visits, hospitalizations, and non-prophylactic gastrostomy tube placements (US sites only) in each treatment group will be tabulated.

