4. STUDY DESCRIPTION

4.1 STUDY DESIGN

This is a Phase 2, double-blind, placebo-controlled, 2-arm, multi-center trial in which subjects will be randomized in a 1:1 ratio to receive either placebo or AG013 in conjunction with their planned course of chemoradiation therapy. Dynamic randomization will be used, with stratification by 3 factors: cisplatin schedule (weekly versus tri-weekly), HPV status (positive versus negative), and geographic region (US versus Europe).

There are 4 study periods as described below: screening, active treatment, short term follow-up and long term follow-up. The screening phase will be no longer than 4 weeks. The active treatment phase will be between 7 and 9 weeks depending on the subject's prescribed CRT plan. The short term follow-up phase will be 4 weeks in duration. The long term follow-up will continue until 12 months post-CRT completion. OM assessments will begin at the start of CRT and continue until the subject has completed short term follow-up or until the OM resolves (as defined by a score of \leq 1 based on WHO criteria), whichever comes first. Long term follow-up will continue for 12 months to assure that AG013 does not adversely impact the tumor response to anti-neoplastic therapy.

A subject's Investigational Medicinal Product (IMP) treatment assignment (AG013 or placebo) will be randomized 1:1 as follows:

- Arm A: Placebo tid
- Arm B: AG013, 2 x 10¹¹ colony forming unit (CFU)/15 mL tid

Screening	Randomization must occur within 4 weeks of the initiation of		
Phase	screening		
Active	Start: Day 1 of CRT		
Treatment	Completion: Day 14 Post-CRT		
Phase	Duration: 7 to 9 weeks depending on the duration of CRT		
Short Term	Start: Day 15 Post-CRT		
	Completion: Day 42 Post-CRT (± 3 days)		
Follow-up	Duration: 4 weeks		

Table 1. Study Periods

	Of note: For patients with persistent grade 2 oral mucositis at week		
	6 post-treatment, follow-up will continue until oral mucositis		
	decreases to grade 1 or less.		
Long Term Follow-up	3, 6 and 12 months (\pm 14 days) post the last dose of CRT		

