7.3 MODIFIED INTENT-TO-TREAT (MITT) POPULATION

The mITT population, defined as all ITT subjects who receive at least 1 dose of IMP and have at least 1 post baseline OM assessment, will be used for all primary and secondary efficacy endpoints. As with the ITT population, subjects will be analyzed in accordance with the treatment arm assigned at randomization.

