8.7.4 EXPLORATORY EFFICACY ENDPOINTS

Exploratory efficacy analyses will be conducted for the mITT population only. The effects of AG013 will be explored on the basis of the following:

Descriptive statistics will be presented for the incidence of severe OM (WHO grades 3 or 4) within subgroups receiving each of the following cumulative radiation doses: <=30 Gy, >30 and <= 40 Gy, >40 and <= 50 Gy, >50 and <= 60 Gy, and > 70 Gy. As with the secondary endpoint analysis, incidence will be defined as the proportion of subjects in each subgroup having at least one grade 3 or 4 OM assessment.

The distribution of OM severity grades at each visit will be provided for CTC and RTOG rating scales. These summary tables will display the number and percentage of patients per OM grade at each visit, by treatment group, for the mITT population.

For each subject, oral mucositis severity scores (WHO grades 0-4) at each time point will be used to calculate AUC using the trapezoidal rule. Average severity-by-time curves will

be generated and plotted for each treatment group, and compared using the Wilcoxon rank-sum test. Descriptive statistics for AUC values will be presented.

Incidence, duration and time to onset of grades 3 and 4 and grades 2, 3, and 4 OM as per NCI CTCAE and RTOG criteria will be analyzed separately, using the same methodology as described for the primary and secondary endpoints. Listings of NCI CTCAE and RTOG grades will be prepared, as well as listings of the calculated endpoints.

Frequency and duration of RT interruptions: The number of subjects in each treatment group with an unplanned break in RT during the 7- to 9-week regimen will be tabulated. Subjects with an interval of 5 days or more without an administration of RT, or who discontinue RT prior to completing the planned RT regimen, will be considered to have an unplanned break in RT. The duration of unplanned RT interruptions (in days) will also be summarized by treatment group using descriptive statistics. For subjects who prematurely discontinue RT, the time from the last dose of RT to the prescribed end date of the regimen will be used in the calculation.

All the RT data will be listed. Calculated values for the above listed endpoints will be listed separately.

The number of unplanned office visits, ER visits, hospitalizations, and non-prophylactic gastrostomy tube placements (US sites only) in each treatment group will be tabulated.

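### The OM severity AUC has no common window and no stated rule for grades after withdrawal, so a literal calculation favours the arm that loses more subjects

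*SAP*

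**What the plan says.** SAP 8.7.4 takes each subject's WHO grades, which "at each time point will be used to calculate AUC using the trapezoidal rule". Average severity curves are then to "be generated and plotted for each treatment group, and compared using the Wilcoxon rank-sum test". Protocol 10.5 has the same plan: "Average AUC severity-by-time curves will be generated and plotted for each treatment group, and compared using the Wilcoxon rank-sum test". I read the test as applied to the per-subject AUC values.

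Neither section states a start day, an end day, a standardisation for time observed, or a fill rule after withdrawal. Neither names strata for the test.

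Three other provisions bear on the point:

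- **Population.** "Exploratory efficacy analyses will be conducted for the mITT population only". Under SAP 7.3 the mITT set requires one dose of IMP, and subjects must "have at least 1 post baseline OM assessment, will be used for all primary and secondary efficacy endpoints". Very early leavers are therefore included.
- **Length of follow-up.** It varies by design. SAP 4.1 states: "OM assessments will begin at the start of CRT and continue until the subject has completed short term follow-up or until the OM resolves". It also states: "The active treatment phase will be between 7 and 9 weeks depending on the subject's prescribed CRT plan".
- **Missing OM data.** SAP 8.3 allows multiple imputation of missing OM assessments if needed, without naming a model, endpoint or end day, and points to SAP 8.7.1 for algorithms. Those algorithms are written for the duration of severe OM.

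**The concern.** WHO grades are never negative, so a trapezoidal area built from observed visits cannot fall as follow-up lengthens. A subject who leaves before mucositis builds has a small area and ranks among the best outcomes, whatever happened afterwards. If one arm loses more subjects than the other, that arm looks better with no treatment effect at all.

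The plan deals with incomplete follow-up elsewhere. SAP 8.7.1 carries unresolved severe OM to Day 91 for the primary endpoint, and a sensitivity analysis there imputes a duration for subjects without severe OM who left early. The AUC has no counterpart, so two programmers could derive materially different values from the same text.

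The test raises a second, separate matter. Every other treatment test named in SAP 8.7 is stratified by cisplatin schedule, HPV status and region. The AUC test is not.

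**Working it through.** The documents give no mean, SD, power or sample size for the AUC, so there is no figure of the plan's own to reproduce.

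**1. One illustrative course (assumed).** The grade rises linearly to 3 by Day 28, stays there to Day 56 and falls to 0 by Day 77.

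- Completer: 3×28/2 + 3×28 + 3×21/2 = 42 + 84 + 31.5 = 157.5 grade-days.
- Leaver at Day 21, where the grade is 3×21/28 = 2.25: 2.25×21/2 = 23.6 grade-days.

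The leaver scores 23.6/157.5 = 15% of the completer's area on an identical course.

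**2. Simulation with no treatment effect.** From the documents: 1:1 allocation and about 200 enrolled (100 per arm), visits twice weekly then weekly, the Day 91 horizon of SAP 8.7.1, a two-sided 5% test, and placebo incidence of severe OM of 75% as a guide (the simulated course gives 79%). Assumed: withdrawal of 10% to 30% per arm, uniform over Days 14 to 49 and unrelated to severity. The protocol implies only 1 − 160/200 = 20% non-evaluable overall, not by arm, and non-evaluable is not the same as lost to OM assessment. All completers are followed to Day 91. Rejection rates (%) by Wilcoxon over 4,000 trials:

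| Withdrawal, AG013 / placebo | AUC to last visit | AUC per day observed | Day 0–91, last grade carried forward | Complete data |
|---|---|---|---|---|
| 20% / 20% | 5.0 | 5.2 | 4.6 | 4.8 |
| 20% / 10% | 22.7 | 17.0 | 5.8 | 5.1 |
| 25% / 15% | 23.7 | 17.4 | 5.7 | 4.9 |
| 30% / 10% | 67.2 | 49.4 | 6.6 | 5.3 |

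Where withdrawal is unequal, nearly all the rejections in the AUC-to-last-visit column favour the arm with more withdrawals.

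**3. Hand check of the shift.** In this course the mean full AUC is 136.3 grade-days (SD 41). Mean area for leavers at Days 21, 28, 35, 42 and 49 is 2.5, 9.8, 23.0, 40.7 and 60.4; at Day 14 it lies between 0 and 2.5. Averaging over Days 14 to 49 in five 7-day steps:

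- Lower bound: (0 + 2.5 + 9.8 + 23.0 + 40.7 + 60.4/2)/5 = 106.2/5 = 21.2.
- Upper bound: (106.2 + 2.5/2)/5 = 21.5.

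A 10-point gap in withdrawal should shift the mean difference by about 0.10 × (136.3 − 21.2) = 11.5 grade-days, and a 20-point gap by 23.0. The simulation gives 11.6 and 23.0.

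**4. A second set of assumptions.** With visits every 3.5 days, withdrawal over Days 7 to 56 and 3,000 trials, false rejection was 21% at 20%/10% and 39% at 25%/10%. Dividing by follow-up time left 12% at 20%/10%, against 17% in step 2.

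**5. Stratification alone.** Settings: normal outcomes, eight strata exactly balanced by arm, an effect of 0.4 residual SD, 3,000 trials. Weak strata effects span ±0.45 SD and strong ones ±1.05 SD.

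| Strata effects | Null rejection (%), Wilcoxon / stratified | Power (%), Wilcoxon / stratified |
|---|---|---|
| Weak | 4.7 / 5.4 | 76.8 / 77.6 |
| Strong | 1.4 / 4.4 | 63.9 / 77.8 |

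The power loss is 77.6 − 76.8 = 0.8 points and 77.8 − 63.9 = 13.9 points.

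**The case against.** The strongest reply is that the plan never says the AUC ends at the last visit. SAP 8.3 provides for imputing missing OM assessments and does not confine that to the primary endpoint. This stands as far as it goes. A reader might infer that early leavers are definitely scored on their observed visits only, but the documents do not say so. What they lack is any statement of whether SAP 8.3 applies to the AUC, with what model, and up to which day. Without an end day, imputation has no target.

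Other tempting extensions also fail:

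- **Stratification as a source of the bias.** Omitting the strata does not make early leavers look better. With balanced strata it makes the test conservative and less powerful.
- **Longer follow-up of persistent OM.** Those subjects have worse mucositis and should rank worse. Stopping at resolution removes only grades of 1 or less.
- **Rinse burden as a cause of unequal withdrawal.** Placebo is also rinsed three times daily and is matched for appearance and taste. Stopping the rinse is not the same as leaving OM assessment: protocol 4.4 continues follow-up examinations where possible, and protocol 6.3.1 requires an oral assessment on the day of withdrawal.
- **Borrowing the primary endpoint's multiple imputation.** SAP 8.7.1 specifies none. Its main rules are deterministic, and its worst-adjacent rule reduces to the last grade after withdrawal because no later value exists.

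**Conclusion.** The point holds as a specification gap with a predictable direction of bias. If the AUC is computed on observed visits, subjects who leave early rank as good outcomes, and the arm with more withdrawals is favoured. The direction follows from non-negative grades and from severity building late in treatment.

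The size is conditional on assumptions outside the documents: the withdrawal rates by arm, their timing and the OM course. At 20% against 10%, false rejection is about 21% to 23%; if withdrawal is equal, the test keeps its 5% level. Nothing in the documents shows that withdrawal will differ.

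The missing stratification is a lesser matter of efficiency, worth about 1 to 14 points of power in the scenarios tried. A reader might infer that the trial's main efficacy claim is at risk. It is not: the AUC is exploratory, is analysed in mITT only and sits outside the hierarchy.

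**What to change.** Amend SAP 8.7.4 before unblinding:

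1. Compute the AUC for every subject over one window, from start of CRT to Day 91, the horizon already used in SAP 8.7.1. Assessments after Day 91 do not enter.
2. Carry the last grade forward to Day 91 after withdrawal, after resolution and after the end of scheduled follow-up. The last case needs stating because an active phase of 7 to 9 weeks plus 4 weeks ends at week 11 to 13, that is Day 77 to Day 91, so many completers have no grades to Day 91.
3. Add multiple imputation under SAP 8.3 as a sensitivity analysis, with its model written down.
4. Compare arms with the stratified CMH test on modified ridit scores, as for the primary endpoint.

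Dividing the area by days observed is not a substitute.

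The cost is wording and a little programming; no new data are needed. The downside is reliance on an assumption about unobserved grades. Carrying the last grade forward can still understate severity in subjects who leave before mucositis builds: in the simulation a shift of about 2 grade-days remained at 20%/10% and 3.6 at 30%/10%, with rejection of 5.8% and 6.6%. That is the reason for the sensitivity analysis.

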8.8 SAFETY ENDPOINTS AND ANALYSIS

All the analyses in this section will be performed on SAF population. Subjects will be analyzed according to the actual treatment they have received.

8.8.1 EXPOSURE TO STUDY TREATMENT

Extent of exposure data were obtained from weekly patient accountability data (used vs. unused vials) as well as from patient diaries in which subjects recorded each of 3 daily administrations of IMP and any missed doses on a daily base. For Extent of exposure analyses diary data will be used, containing the most detailed information, i.e. daily dosing information. Total duration of exposure to study drug will be summarized for each treatment group. Total duration of exposure to treatment will be defined as the time from first to last use of the IMP (in days). Specifically, extent of exposure = last dose date – first dose date + 1. The total number of doses planned will be calculated as the sum all doses that should have been taken according to the assigned dose regimen (i.e. total duration of exposure x 3). Total percent of doses received will be calculated as the cumulative actual doses divided by the cumulative planned doses, expressed as percentage. Number of planned doses will be calculated by taking the minimum of date

of last dose minus date of first dose plus one times three. Total number of days with at least one dose per day will also be summarized.

Summaries of the number of missed doses and percent of doses received will also be prepared per week, the last week of treatment and overall. Doses will be considered missed if either the eCRF indicates the dose was missed or there is no record for a particular administration before the end of treatment or discontinuation. Number of missed doses will be calculated as the number of doses assigned minus the number of doses taken, and percent of doses received will be calculated as the number of doses taken divided by number of doses planned. Total number of days per week with at least one dose per day will be calculated, and summary of percent of days per week with at least one dose taken will be prepared.

Separate summary tables for IMP taste, consistency, and smell will be created. Weekly averages will be calculated using daily reports. Missing assessments will be excluded from estimation.

Summaries will be displayed by treatment and by week.

A listing of exposure to the study drug will be created, including dose, taste, consistency and smell. Calculated weekly averages will be listed as well.

Details on radiation therapy plan (location of tumor, prescribed cumulative dose and treated sites) will be summarized. Cumulative actual exposure to RT will also be summarized. Dose delays and changes will be listed together with the reasons for delays/changes.

A listing of RT data and RT plan will be provided.

Cumulative exposure to chemotherapy (Cisplatin) will be summarized by timepoint. Dose delays and changes and the reasons for them will be summarized as well.

A listing of chemotherapy data will be created.

8.8.2 ADVERSE EVENTS

All AEs will be coded by PT and SOC using MedDRA version 19.0 or higher. The NCI-CTCAE (Version 4.03) will be used to grade both clinical and laboratory AEs.

The incidence of TEAEs will be summarized by treatment group and tabulated by SOC and Preferred Term (PT). A TEAE is defined as an AE that first occurs or worsens in severity on or after the first dose of the IMP until end of short term follow-up. Summary tables will include all TEAEs. Incomplete starting dates of AEs will be imputed using the rules from section 8.3 of this SAP. TEAEs will be further summarized by severity (grade) and relatedness to IMP. Each AE (based on PT) will be counted only once for a given

subject. If the same AE occurs on multiple occasions, the highest severity and strongest relationship will be assumed. If 2 or more AEs are reported as a unit, the individual terms will be reported as separate events. AE severity will not be imputed if missing.

Summaries and by-patient data listings of TEAEs, AEs leading to death, SAEs, and AEs leading to discontinuation will be provided. The by-patient AE data listings will include onset and resolution dates, verbatim term, PT, treatment, severity (grade), relationship to treatment, action taken for the event, and outcome. All the deaths, including those reported during the long-term follow-up period, will be listed with the primary causes.

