6.2 Safety Assessments

Safety will be assessed by collecting and recording Adverse Events (AEs) (Section 8.4) and laboratory assessments and the presence of sAGX0085 in whole blood.

The study will utilize local laboratories for safety assessments, the samples intended for the presence of sAGX0085 in whole blood will be analyzed by Intrexon Actobiotics. The clinical laboratory will indicate laboratory values out of normal ranges. The Investigator must assess all abnormal clinical laboratory results for clinical significance in a timely fashion. Laboratory specimens will be collected at specific time points throughout the duration of the study. A notation of clinically significant (CS) or non-clinically significant (NCS) with initials and date will be documented on the respective laboratory report next to any abnormal value. An abnormal clinical laboratory value will be considered and documented as an AE, if in the opinion of the Investigator, it is clinically significant. The Investigator will follow proper adverse event reporting procedures. Should the site process for indicating CS/NCS lab values not be in accordance with the above, site will provide written procedure for assessing CS lab values and follow stated process throughout study.

Body weight, KPS, and vital signs, including temperature, systolic and diastolic blood pressures, heart rate and respiration rate, will be measured and recorded at the screening and baseline visits, once weekly during the active treatment phase and at the End of Active Treatment Phase Visit. All vital signs should be measured after two minutes of rest in the sitting position.

This document contains confidential information. It is intended solely for the use of the principal investigator, co-investigators, staff, appropriate institutional review boards or ethical committees, and other required regulatory bodies.

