8.4 Recording of Adverse Events

All AEs encountered during the clinical study will be recorded in detail in the source documents and documented in the eCRF, from signature of the ICF through the end of the short term follow-up phase. All AEs that meet the seriousness criteria (Section 8.6) should

This document contains confidential information. It is intended solely for the use of the principal investigator, co-investigators, staff, appropriate institutional review boards or ethical committees, and other required regulatory bodies.

also be recorded on the SAE Report Form. All SAEs must be reported to the sponsor or delegated organization within the timeline stated in Section 8.7.

The recording of AEs will be based on data obtained from the following sources:

- Medical and surgical history
- Physical examinations including vital signs
- Clinical laboratory test results
- Subject diary

All clinical events, including both observed (such as any reaction at sites of application) and volunteered problems, complaints, or symptoms, are to be recorded. The need to capture this information is not dependent upon whether the clinical event is associated with the use of any IMP.

Clinical symptoms or events such as mucositis or stomatitis are not to be recorded as an AE or SAE.

Clinically significant bacteremia and clinical sepsis should be recorded as AE or SAE.

The potential adverse event profile of the IMP regimen is located in Appendix H.

If at anytime during the study a subject develops symptoms suggesting clinically significant bacteremia that can be attributed to sAGX0085 (as determined by three consecutive positive blood cultures), study treatment will be discontinued.

In the event that a subject develops symptoms suggesting clinically significant bacteremia or sepsis, the subject should be treated per the site's standard of care. Prior to treatment of the event, 3 consecutive whole blood samples need to be taken from the subject and aliquots of these samples must be sent immediately to Intrexon Actobiotics for analysis. The first two samples are to be drawn together and the third sample is to be drawn 10-15 minutes after the first tube is drawn. Detailed information can be found in the laboratory manual.

A disposition plan for the management of clinical sepsis is provided in appendix I.

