8.10 Regulatory Reporting of Adverse Events

If there are serious, unexpected adverse drug reactions (for Europe, SUSAR: Suspected Unexpected Serious Adverse Reaction) associated with the use of the IMP, the appropriate regulatory agency(ies) and all participating investigators will be notified in accordance with the following Guidance for Industry: Clinical Safety Data Management: Definitions and

This document contains confidential information. It is intended solely for the use of the principal investigator, co-investigators, staff, appropriate institutional review boards or ethical committees, and other required regulatory bodies.

Standards for Expedited Reporting (ICH-E2A), Detailed Guidance on the Collection, Verification and Presentation of Adverse Event/Reaction Reports Arising from Clinical Trials on Medicinal Products for Human Use (CT-3). Clinically significant bacteremia and clinical sepsis associated with the use of the IMP will also be reported on an expedited basis.

It is the responsibility of the investigator to promptly notify the Institutional Review Board (IRB)/Independent Ethics Committee (IEC) of all unexpected serious adverse drug reactions involving risk to human subjects. An unexpected event is one that is not reported in the current Investigator's Brochure.

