Clinical laboratory data will be presented for each treatment group using descriptive statistics based on the observed values and change from baseline values at each scheduled visit. Summary statistics (n, mean, median, SD, minimum, and maximum) will be calculated for quantitative safety data and frequency counts will be compiled for classification of qualitative safety data. Shift tables from baseline to the worst post-baseline values during the treatment period will be provided for chemistry parameters and hematology parameters that have NCI-CTCAE v4.03 toxicity grades. Both scheduled and unscheduled post baseline values during the treatment period will be considered. Additionally, the number and percentage of subjects with Grade \geq 3 will be presented for each CTCAE gradable laboratory test.

All clinical laboratory data will be listed by subject. Values outside the normal ranges will be flagged and toxicity grades will be displayed for relevant parameters.

To assess IMP tolerability, average daily ratings of IMP taste, consistency, and smell will be summarized descriptively, by week, for each treatment group.

Pre-study abnormalities and reported abnormalities at the end of active treatment will be tabulated by body system. Changes in physical examinations will be described in the text of the final study report.

Prior and concomitant medications will be coded using the WHO dictionary. These data will be tabulated for each treatment group; details regarding dose regimens and start/stop dates will be presented in by-subject data listings.

The number and percentage of subjects with presence of AG013-sAGX0085 bacteria will be summarized by treatment group.

Tumor response assessments will be summarized descriptively at each timepoint (3, 6, and 12 months following the last dose of CRT).

This document contains confidential information. It is intended solely for the use of the principal investigator, co-investigators, staff, appropriate institutional review boards or ethical committees, and other required regulatory bodies.

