Appendix H: Potential Adverse Event Profile of the IMP Regimen

Relative to the risk of clinical sepsis due to the study organism, the study organism is nonpathogenic, preclinical safety studies failed to show any evidence for clinical sepsis even after intravenous administration of the study organism in severely neutropenic animals, and subjects in other clinical trials of a similar mucosally administered non-pathogenic organism have not demonstrated bacteremia or sepsis. No patients of the phase 1b study AG013-ODOM-101 (a group that was myelosuppressed) developed sepsis from AG013 nor could AG013 be detected in the blood. No deaths or discontinuations due to AEs occurred in this study.

The chances of AG013 adversely affecting the course of oral mucositis seem equally remote. Preclinical studies have shown a clear beneficial effect on severity and duration of oral mucositis in a relevant animal model. In addition, results of a clinical study in which another form of topically administered trefoil factor was tested demonstrated its benefit in modulating the course and severity of oral mucositis. Several efficacy endpoints were measured as exploratory endpoints in the phase 1b AG013-ODOM-101 study. Subjects who received AG013 had a lower percentage of days with ulcerative mucositis, and more subjects who received AG013 on any dosing schedule had no or only 1 day of ulcerative mucositis compared to subjects who received placebo.

Within the intended study population, there is no particular population at risk, and the risks are not predictable or preventable.

Clinical sepsis due to the study organism is reversible and time-limited when antibiotic therapy is applied. Worsening of mucositis is reversible and time-limited.

Following adverse events linked to the IMP regimen can potentially occur:

- Clinically significant bacteremia
- Clinical sepsis

This document contains confidential information. It is intended solely for the use of the principal investigator, co-investigators, staff, appropriate institutional review boards or ethical committees, and other required regulatory bodies.

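### The SAP specifies no pooled by-arm count of subjects with bacteremia or sepsis, the only AEs the protocol links to AG013, and its safety section omits the protocol's sAGX0085 count

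*SAP*

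**What the plan says.** **The harm is identified in advance.** Protocol Appendix H introduces its list with "Following adverse events linked to the IMP regimen can potentially occur" and gives two entries, clinically significant bacteremia and clinical sepsis. Protocol 8.4 adds: "Clinically significant bacteremia and clinical sepsis should be recorded as AE or SAE". Protocol 8.10 states: "Clinically significant bacteremia and clinical sepsis associated with the use of the IMP will also be reported on an expedited basis". Protocol 11.4 has the DSMB Charter describe expedited review of both events. Protocol 10.10 and SAP 4.3 contain a stopping rule for clinical sepsis attributed to sAGX0085.

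**The AE analysis is generic.** SAP 8.8.2 states: "The incidence of TEAEs will be summarized by treatment group and tabulated by SOC and Preferred Term (PT". The counting rule is "Each AE (based on PT) will be counted only once for a given" subject. AEs reported as a unit are split into separate events. TEAEs are also summarised by grade and relatedness, and the section adds: "Summaries and by-patient data listings of TEAEs, AEs leading to death, SAEs, and AEs leading to discontinuation will be provided". Neither document defines a grouped term, a standardised query or an AE of special interest for bacteremia and sepsis.

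**The organism is handled differently in the two documents.** Protocol 6.2 includes "the presence of sAGX0085 in whole blood" among the safety assessments, and Protocol 10.6 plans: "The number and percentage of subjects with presence of AG013-sAGX0085 bacteria will be summarized by treatment group". SAP 8.8 contains no such count. SAP 8.9.1 describes blood levels of the bacteria under PK, in a consenting subset with a target of 15 per arm. SAP 9 lists three departures from the protocol, and this is not one of them.

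**The concern.** The protocol gives these two events their own recording instruction, expedited reporting when associated with the IMP, DSMB procedures, a stopping rule and a management appendix. The analysis then treats them like any other AE. A reader of the report would want to know how many subjects in each arm had bacteremia or sepsis, and no specified table answers that directly.

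This matters because an excess could be coded to more than one PT and become harder to see row by row. If terms are pooled only after unblinding, the choice of terms is open to selection. The randomised by-arm comparison is also the one piece of evidence that does not depend on anyone's judgement of cause. The relatedness table, the stopping rule and the organism tests all address events attributed to the product. An excess of bacteremia or sepsis not attributed to sAGX0085 would show only in an all-cause comparison.

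**Working it through.** The plan states no figure on this point, so there is none to reproduce. The finding rests on the text; the arithmetic only illustrates it.

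**Step 1: what each planned output gives.**
- PT row: a by-arm subject count for that PT. Rows overlap when a subject has two PTs, so their sum is events by term, not subjects.
- SOC row: a wider category that can mix these events with unrelated ones in patients on cisplatin and radiation.
- Grade, relatedness and SAE summaries: further cuts of the same AE data. No grouped term is defined for them either.
- By-patient listings: anyone can count subjects from them, but the term list and the count are not specified.
- DSMB review and stopping rule: controls during conduct, not a reported incidence.
- Protocol 10.6 organism count: specific to sAGX0085, and absent from the SAP safety section.

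**Step 2: illustration inputs.** About 200 subjects enrolled (Protocol 4.1), randomised 1:1, so 200/2 = 100 per arm. Event rates are assumptions. Protocol Appendix I calls the magnitude unknown and the probability likely extremely small.

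**Step 3: formula.** The chance that a row reaches two-sided Fisher p ≤ 0.05 is the sum over x and y of Bin(x; 100, pA) × Bin(y; 100, pP) × 1[Fisher p(x, y) ≤ 0.05]. For an even split over three PTs with one PT per subject, each row has rates pA/3 and pP/3. If r is the chance for one row, the chance for any row is approximately 1 − (1 − r)³. Results use unrounded r.

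| Assumed rates, AG013 v placebo | One pooled row | One of three rows (r) | Any of three rows |
|---|---|---|---|
| 10% v 2% | 58.7% | 6.7% | 18.8% |
| 12% v 3% | 61.2% | 9.6% | 26.2% |
| 8% v 1% | 56.8% | 3.8% | 11.1% |
| 15% v 5% | 58.6% | 12.1% | 32.1% |

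Check for 10% v 2%: 1 − (1 − 0.067)³ = 1 − 0.812 = 0.188.

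**Step 4: sensitivity to the split, 10% v 2%, any row significant against AG013 (simulation).**
- Five even PTs: about 5%.
- Three even PTs: about 19%.
- Two even PTs: about 35%.
- Three PTs split 70/20/10: about 37%.
- Three PTs split 80/10/10: about 44%.
- Every affected subject coded to two of three PTs: about 58%, essentially no loss.

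**Step 5: one data set.** 10 v 2 subjects gives p = 0.033. The same subjects in rows of 4 v 1, 3 v 1 and 3 v 0 (4+3+3 = 10; 1+1+0 = 2) give p = 0.37, 0.62 and 0.25.

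**The case against.** The strongest reply is that the by-arm data are already reported. A sepsis row and a bacteremia row each give an incidence by arm. There are SOC, grade, relatedness and SAE summaries, and listings with verbatim term, PT and treatment. Every SAE goes to the DSMB, which receives unblinded data for such events. Suspected bacteremia or sepsis prompts three whole-blood samples for organism analysis (Protocol 8.4). This stands. A reader might infer that the report will contain no by-arm incidence of these events, or that an excess would be hidden. The documents do not support either reading.

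Second, Appendix H discusses sepsis due to the study organism, whereas a pooled clinical row is all-cause and so mixes causes too. That is a fair limit. The all-cause row is worth having because it needs no attribution, and the organism count in Protocol 10.6 is its natural companion. That companion is missing from the SAP safety section.

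Third, the illustration depends on unsourced rates and on how events split. Uneven splits lose less, and double coding may lose almost nothing. No AE test is planned, so Fisher power is only a proxy for how visible a difference is. The documents name two terms and ask for standard medical terminology; they do not show that sites will use many. All of this stands.

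Fourth, SAP 2 places the table list in a separate mock TFL document, which was not available for this review. A grouped table there cannot be ruled out. Even so, the definition and term list belong in the SAP.

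**Conclusion.** The point holds as a low-cost improvement, not as an error in the analysis. Two statements are supported.

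1. The protocol names bacteremia and sepsis as the only AEs potentially linked to the IMP, and the SAP specifies no pooled by-arm count of subjects with either. PT counting means that count cannot be had by adding rows.
2. The by-arm sAGX0085 count in Protocol 10.6 is absent from SAP 8.8 and not declared in SAP 9. This is a plain discrepancy between the documents and needs no assumption.

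The size of the first is uncertain. Under 10% v 2% and 100 per arm, the chance of a visibly extreme row falls from about 59% pooled to about 19% with three even PTs or about 37% with a 70/20/10 split. It hardly falls if most subjects carry two PTs. These figures rest on assumed rates and coding patterns. If the true rate is very small, as Appendix I expects, neither presentation would separate the arms statistically; the pooled row would still give a clear count and an interval.

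**What to change.** In SAP 8.8.2:
- Define a grouped bacteremia/sepsis category, with its PT list settled by blinded review before the first database lock. SAP 8.5 already makes the final determination of major deviations before lock, so the step fits the existing process. AE recording ends with short term follow-up, so the table can be produced at that lock.
- Report by arm in the SAF set the number and percentage of subjects with at least one such event, for all events and for serious ones, with the risk difference and an exact 95% CI.
- Add a listing with relatedness and any available sAGX0085 blood result.
- Keep the SOC/PT table.

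In SAP 8.8, restore the Protocol 10.6 count of subjects with sAGX0085 present and name the specimen it refers to, or list its omission with a reason in SAP 9.

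The cost is SAP wording, a blinded term review, one table and one listing. The listing also needs linkage to organism results, which are analysed outside the local safety laboratories. No new procedure or sample is required, and no clinical rule changes. The pooled row will include events not caused by the study organism, and a footnote should say so.
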